5.4 IMMEDIATE REPORTING REQUIREMENTS FROM INVESTIGATOR TO SPONSOR

Certain events require immediate reporting to allow the Sponsor to take appropriate measures to address potential new risks in a clinical trial. The investigator must report such events to the Sponsor immediately; under no circumstances should reporting take place more than 24 hours after the investigator learns of the event. The following is a list of events that the investigator must report to the Sponsor within 24 hours after learning of the event, regardless of relationship to study treatment:

- Serious adverse events (defined in Section 5.2.2; see Section 5.4.2 for details on reporting requirements)
- Adverse events of special interest (defined in Section 5.2.3; see Section 5.4.2 for details on reporting requirements)

- Pregnancies (see arm-specific appendices for details on pregnancy reporting requirements for each treatment arm)

For serious adverse events and adverse events of special interest, the investigator must report new significant follow-up information to the Sponsor immediately (i.e., no more than 24 hours after becoming aware of the information). New significant information includes the following:

- New signs or symptoms or a change in the diagnosis
- Significant new diagnostic test results
- Change in causality based on new information
- Change in the event's outcome, including recovery
- Additional narrative information on the clinical course of the event

Investigators must also comply with local requirements for reporting serious adverse events to the local health authority and IRB/EC.

5.4.1 Medical Monitors and Emergency Medical Contacts

To ensure the safety of study patients, access to the Medical Monitors is available 24 hours per day, 7 days per week. Details will be provided separately.

5.4.2 Reporting Requirements for Serious Adverse Events and Adverse Events of Special Interest

5.4.2.1 Events That Occur prior to Study Treatment Initiation

After informed consent has been obtained but prior to initiation of study treatment, only serious adverse events caused by a protocol-mandated intervention should be reported. The paper Clinical Trial Adverse Event/Special Situations Form provided to investigators should be completed and submitted to the Sponsor or its designee immediately (i.e., no more than 24 hours after learning of the event), either by faxing or by scanning and emailing the form using the fax number or email address provided to investigators.

5.4.2.2 Events That Occur after Study Treatment Initiation

After initiation of study treatment, serious adverse events and adverse events of special interest will continue to be reported until 135 days after the final dose of study treatment or until initiation of new systemic anti-cancer therapy, whichever occurs first.

Investigators should record all case details that can be gathered immediately (i.e., within 24 hours after learning of the event) on the Adverse Event eCRF and submit the report via the electronic data capture (EDC) system. A report will be generated and sent to Roche Safety Risk Management by the EDC system.

In the event that the EDC system is unavailable, the paper Clinical Trial Adverse Event/Special Situations Form provided to investigators should be completed and submitted to the Sponsor or its designee immediately (i.e., no more than 24 hours after learning of the event), either by faxing or by scanning and emailing the form using the

fax number or email address provided to investigators. Once the EDC system is available, all information will need to be entered and submitted via the EDC system.

Instructions for reporting serious adverse events that occur after the reporting period are provided in Section 5.6.

5.5 FOLLOW-UP OF PATIENTS AFTER ADVERSE EVENTS

5.5.1 Investigator Follow-Up

The investigator should follow each adverse event until the event has resolved to baseline grade or better, the event is assessed as stable by the investigator, the patient is lost to follow-up, or the patient withdraws consent. Every effort should be made to follow all serious adverse events considered to be related to study treatment or trial-related procedures until a final outcome can be reported.

During the study period, resolution of adverse events (with dates) should be documented on the Adverse Event eCRF and in the patient's medical record to facilitate source data verification.

All pregnancies reported during the study should be followed until pregnancy outcome.

5.5.2 Sponsor Follow-Up

For serious adverse events, adverse events of special interest, and pregnancies, the Sponsor or a designee may follow up by telephone, fax, electronic mail, and/or a monitoring visit to obtain additional case details and outcome information (e.g., from hospital discharge summaries, consultant reports, autopsy reports) in order to perform an independent medical assessment of the reported case.

5.6 ADVERSE EVENTS THAT OCCUR AFTER THE ADVERSE EVENT REPORTING PERIOD

After the end of the reporting period for serious adverse events and adverse events of special interest (defined as 135 days after the final dose of study treatment or until initiation of new, systemic anti-cancer therapy, whichever occurs first), all deaths, regardless of cause, should be reported through use of the Long-Term Survival Follow-Up eCRF.

After the end of the reporting period for non-serious adverse events (defined as 30 days after the final dose of study treatment), all treatment-related non-serious adverse events that lead to surgery delay will continue to be reported until 135 days after the final dose of study treatment.

In addition, if the investigator becomes aware of a serious adverse event that is believed to be related to prior exposure to study treatment, the event should be reported through use of the Adverse Event eCRF. However, if the EDC system is not available, the investigator should report these events directly to the Sponsor or its designee, either by

faxing or by scanning and emailing the paper Clinical Trial Adverse Event/Special Situations Form using the fax number or email address provided to investigators.

5.7 EXPEDITED REPORTING TO HEALTH AUTHORITIES, INVESTIGATORS, INSTITUTIONAL REVIEW BOARDS, AND ETHICS COMMITTEES

The Sponsor will promptly evaluate all serious adverse events and adverse events of special interest against cumulative product experience to identify and expeditiously communicate possible new safety findings to investigators, IRBs, ECs, and applicable health authorities based on applicable legislation.

To determine reporting requirements for single adverse event cases, the Sponsor will assess the expectedness of these events through use of the reference safety information in the documents listed below:

- Opdivo® EMA Summary of Product Characteristics (SmPC; nivolumab)
- Yervoy® EMA SmPC (ipilimumab)
- RO7247669 Investigator's Brochure
- Atezolizumab Investigator's Brochure
- Tiragolumab Investigator's Brochure

The Sponsor will compare the severity of each event and the cumulative event frequency reported for the study with the severity and frequency reported in the applicable reference document.

Reporting requirements will also be based on the investigator's assessment of causality and seriousness, with allowance for upgrading by the Sponsor as needed.

6. STATISTICAL CONSIDERATIONS AND ANALYSIS PLAN

The final study analysis will be based on patient data collected through study discontinuation. If not otherwise specified, efficacy analyses will be based on the efficacy-evaluable population, defined as all patients who receive at least one dose of each drug for their assigned treatment regimen, and safety analyses will be based on the safety-evaluable population, defined as all patients who receive any amount of study treatment.

The analysis results will be summarized by the treatment that patients actually receive. Data will be described and summarized as warranted by sample size. Continuous variables will be summarized through use of means, standard deviations, medians, and ranges. Categorical variables will be summarized through use of counts and percentages. Listings will be used in place of tables in the event of small sample sizes.

6.1 DETERMINATION OF SAMPLE SIZE

This study is not designed to make explicit power and type I error considerations for a hypothesis test. Instead, this study is designed to obtain preliminary efficacy, safety, and PK data on treatments or treatment combinations when administered to patients with melanoma. Cohort 1 will consist of patients with resectable Stage III melanoma who have not received prior systemic therapy for their disease. Cohort 2 will consist of patients with Stage IV melanoma who experienced disease progression during or after at least one but not more than two lines of treatment for metastatic disease.

In Cohort 1, approximately 195–290 patients will be randomly allocated to the control and experimental arms during the study (35–50 patients to the control arm and 20–60 patients to each experimental arm). In Cohort 2, approximately 8–46 patients will be assigned to an experimental arm. Please refer to [Table 4](#) for further details.

6.2 SUMMARIES OF CONDUCT OF STUDY

Enrollment will be summarized by region, country, and investigator by treatment arm. Patient disposition will be summarized by treatment arm. Major protocol deviations, including major deviations with regard to the inclusion and exclusion criteria, will be summarized by treatment arm.

For safety-evaluable patients, study drug administration data will be tabulated or listed by treatment arm, and any dose modifications will be flagged. Means and standard deviations will be used to summarize the total dose and dose intensity for each study drug. Reasons for discontinuation of study drugs will also be tabulated.

6.3 SUMMARIES OF DEMOGRAPHIC AND BASELINE CHARACTERISTICS

Demographic and baseline characteristics (including age, sex, race/ethnicity, weight, malignancy duration, metastatic disease site [if applicable], and baseline ECOG PS) will be summarized overall and by treatment arm.

6.4 EFFICACY ANALYSES

6.4.1 Primary Efficacy Endpoint in Cohort 1

The primary efficacy endpoint in Cohort 1 is pRR at time of surgery. pRR will be assessed after completion of neoadjuvant treatment (Week 7) at time of CLND.

The pRR is defined as the proportion of patients who achieve pCR (a complete absence of viable tumor in the treated tumor bed), pathologic near complete response (pnCR; <10% of viable tumor in the treated tumor bed); and pathologic partial response (pPR; <50% of the treated tumor bed is occupied by viable tumor cells) as determined by independent pathologic review. Patients with missing or no pathologic response assessment, *including patients who do not proceed to CLND*, will be classified as non-responders.

pRR will be calculated for each arm along with 95% CIs (Clopper-Pearson method). The difference in pRR between the experimental arms and the control arm will also be calculated, along with 95% CIs using the Wald method with continuity correction.

6.4.2 Secondary Efficacy Endpoints in Cohort 1

The secondary efficacy endpoints in Cohort 1 are pRR at time of surgery as determined by local pathologic assessment, event-free survival (EFS), RFS, OS, and ORR prior to surgery. pRR is defined in Section [6.4.1](#).

EFS is defined as the time from randomization to any of the following events (whichever occurs first): disease progression that precludes surgery, as assessed by the investigator according to RECIST v1.1 (see Section [4.5.7](#)); local, regional, or distant disease recurrence; or death from any cause. Patients who have not experienced such events will be censored at the time of their last post-tumor tumor assessment.

RFS is defined as the time from surgery to the first documented recurrence of disease or death from any cause. For patients who do not have documented recurrence of disease or death, RFS will be censored at the day of the last tumor assessment.

OS is defined as the time from randomization to death from any cause. Patients who are still alive at the time of OS analysis will be censored at the last date they were known to be alive.

The Kaplan-Meier method will be used to estimate the median for RFS, EFS, and OS, 95% CIs will be constructed using the Brookmeyer and Crowley method. The RFS, EFS, and OS rate at specific timepoints will also be estimated using the Kaplan-Meier method, with 95% CIs calculated on the basis of Greenwood's estimate for the variance.

The ORR according to RECIST v1.1 will be assessed after completion of neoadjuvant treatment (Week 7) and is defined as the proportion of patients with a CR or PR, as determined by the investigator according to RECIST v1.1. Patients with missing or no response assessments will be classified as non-responders. Note that ORR will be determined using unconfirmed pre-operative radiologic responses. Although RECIST v1.1 requires confirmatory imaging assessments to be completed at least 4 weeks after the initial response, due to the timing of CLND, these responses cannot be confirmed with subsequent imaging.

ORR will be calculated for each arm, along with 95% CIs (Clopper-Pearson method). The difference in ORR between the experimental arms and the control arm will also be calculated, along with 95% CIs using the Wald method with continuity correction.

6.4.3 Exploratory Efficacy Endpoints in Cohort 1

The exploratory efficacy endpoints in Cohort 1 are landmark EFS, landmark RFS, and landmark OS at specific timepoints (1, 2, 3, and 5 years). RFS, EFS, and OS are defined in Section [6.4.2](#).

Landmark EFS rates, landmark RFS rates, and landmark OS rates will be estimated for each study arm using the Kaplan-Meier method, with 95% CIs calculated through use of Greenwood's formula.

6.4.4 Primary Efficacy Endpoint in Cohort 2

The primary efficacy endpoint in Cohort 2 is ORR, as defined in Section [2](#) (see [Table 3](#)). ORR is determined by the investigator according to RECIST v1.1. Patients with missing or no response assessments will be classified as non-responders.

ORR, the proportion of patients with a complete or partial response, will be calculated for each arm, along with 95% CIs (Clopper-Pearson method).

6.4.5 Secondary Efficacy Endpoints in Cohort 2

The secondary efficacy endpoints in Cohort 2 are PFS, OS, OS at specific timepoints (e.g., 6 months), duration of response (DOR), and disease control, as defined in Section [2](#) (see [Table 3](#)). PFS, DOR, and disease control are determined by the investigator according to RECIST v1.1.

DOR will be derived for efficacy-evaluable patients with a CR or PR.

For patients who do not have documented disease progression or death, PFS and DOR will be censored at the day of the last tumor assessment.

Patients who are still alive at the time of OS analysis will be censored at the last date they were known to be alive.

The Kaplan-Meier method will be used to estimate the median for PFS, OS, and DOR, with 95% CIs constructed through use of the Brookmeyer and Crowley method. OS rate at specific timepoints will also be estimated using the Kaplan-Meier method, with 95% CIs calculated on the basis of Greenwood's estimate for the variance.

Disease control rate (the proportion of patients with SD for ≥ 12 weeks), a PR, or a CR, will be calculated for each treatment arm, with 95% CIs estimated through use of Clopper-Pearson's exact method.

6.4.6 Exploratory Efficacy Endpoints in Cohort 2

The exploratory efficacy endpoints are ORR, PFS, DOR, and disease control as determined by the investigator according to iRECIST (see [Appendix 2](#)).

ORR, PFS, DOR, and disease control will be analyzed through use of the same methods described in Sections 6.4.4 and Section 6.4.5. DOR will be derived for efficacy-evaluable patients with a CR or PR.

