1.1.2.1 Neoadjuvant Immunotherapy Treatment in Stage III Melanoma

Nonclinical studies demonstrated improved survival and increased anti-tumor immunity when immune CPI therapy was given before surgery as compared with adjuvant application (Liu et al. 2016; Brockwell et al. 2017; Bourgeois-Daigneault et al. 2018; Brooks et al. 2018; O'Donnell et al. 2019). Patients with clinically detectable Stage III melanoma are ideal candidates for neoadjuvant therapy because they represent a high-risk patient population with poor outcomes when treated with upfront surgery alone. Neoadjuvant therapy also has the advantage of providing information on pathologic response, which is valuable to estimate prognosis and to guide the choice of adjuvant therapy and follow-up (Tetzlaff et al. 2018). Moreover, the availability of tumor tissue before and following therapy enables efficient exploration of possible mechanisms of resistance and response as well as identification of baseline biomarkers. Neoadjuvant therapy for melanoma is now an active area of research, with numerous completed and ongoing trials that have disparate designs, endpoints, and analyses (Menzies et al. 2021). The International Neoadjuvant Melanoma Consortium (INMC) was created by

experts in medical oncology, surgical oncology, pathology, radiation oncology, radiology, and translational research who developed recommendations for investigating neoadjuvant therapy in melanoma to align future trial designs and correlative analyses (Amaria et al. 2019).

Six melanoma neoadjuvant trials were conducted recently with BRAF/MEK-targeted therapy or PD-1-based immunotherapy (reviewed by Amaria et al. 2019). These trials demonstrated that neoadjuvant therapies can achieve high pathologic complete response (pCR) rates and impressive RFS in Stage III melanoma (Menzies et al. 2021; Rozeman et al. 2021). The initial data are particularly promising for the neoadjuvant combination of nivolumab plus ipilimumab. Treatment with nivolumab plus ipilimumab results in pathologic response rates (pRRs) between 70%–80%, is well tolerated, and may reduce surgical morbidity (Rozeman et al. 2019; Blank et al. 2020).

This study protocol was developed in accordance with INMC guidelines to create the needed consistency amongst neoadjuvant trials in order to facilitate optimal data organization for future regulatory review. Its exploratory analysis plan will strengthen translational research across the melanoma disease continuum.

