4.2 METHOD OF TREATMENT ASSIGNMENT

This is a randomized, open-label study. After initial written informed consent has been obtained, all screening procedures and assessments have been completed, and eligibility has been established for a patient, the study site will obtain the patient's identification number and treatment assignment from the interactive web-based response system (IxRS).

For Cohort 1, this study will employ a permuted-block randomization method with dynamically changing randomization ratios to account for fluctuation in the number of treatment arms that are open for enrollment over the course of the study.

The randomization ratio will depend on the number of experimental arms that are open for enrollment (e.g., if an arm is added or enrollment in an arm is suspended pending analysis of results from the preliminary phase), with the stipulation that the likelihood of being allocated to the control arm will be no more than 35%. The randomization ratios may be altered to increase enrollment in a particular arm.

Randomization will be stratified according to the following criteria:

- Geographic region: Australia vs. Rest of the World
- Baseline LDH: \leq ULN vs. $>$ ULN

Randomization will take into account general exclusion criteria and arm-specific exclusion criteria as outlined in Section 4.1.2. For example, the Atezo + Tira arm will be removed as an option for patients who are ineligible for that arm. If a patient is only eligible for the control arm, that patient will not be enrolled in the study.

For Cohort 2, patients will be assigned to receive treatment with RO7247669 2100 mg + Tira. If additional treatment arms are opened at a later time, a permuted-block randomization method will be employed from this point forward.

Patients who do not receive at least one dose of each drug for their assigned treatment regimen will not be included in the efficacy analyses. Additional patients may be enrolled to reach the target number of treated patients planned for analysis.

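### The between-arm pRR and ORR intervals use a continuity-corrected Wald method, with no stratified estimate named, and are about 10–22% wider than a Newcombe interval at the planned arm sizes and expected control rate

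*Combined protocol and SAP*

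**What the plan says.** For the primary endpoint, Section 6.4.1 handles each arm separately ("pRR will be calculated for each arm along with 95% CIs (Clopper-Pearson method") and then gives each experimental arm's difference from control with "95% CIs using the Wald method with continuity correction". Section 6.4.2 repeats the approach for the secondary radiologic endpoint: "The difference in ORR between the experimental arms and the control arm will also be calculated", with the same kind of interval.

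Section 4.2 states "Randomization will be stratified according to the following criteria" and lists two binary factors, region (Australia or elsewhere) and baseline LDH (up to or above the upper limit of normal). Section 3.1.2 names the same two. Section 6 mentions neither factor in any efficacy analysis. The plan never calls the interval unstratified; that is inferred from its silence.

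The Cohort 1 sizes in Section 6.1 are "35–50 patients to the control arm and 20–60 patients to each experimental arm". The same section says "This study is not designed to make explicit power and type I error considerations for a hypothesis test". Section 1.1.2.1 gives the expected control result: "Treatment with nivolumab plus ipilimumab results in pathologic response rates (pRRs) between 70%–80" (that is, 70% to 80%).

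**The concern.** The Wald interval is a large-sample method, and here it would be used with as few as 20 patients in an arm and response rates well above one half. The continuity correction adds a fixed amount to each side that depends only on the arm sizes, so it weighs most in the smallest arms. Score-type intervals (Newcombe, Miettinen-Nurminen) are the usual alternatives at these sizes. If they hold 95% with less width, the plan reports less precision on its primary comparison than the data support.

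Separately, the sponsor chose region and LDH as factors worth balancing. An analysis that leaves them out keeps any chance imbalance in the estimate and gives up whatever precision they carry.

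**Working it through.** The plan states no interval width, coverage or power for these differences, so there is no figure of its own to reproduce.

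**Inputs.** Arm sizes: experimental 20, 40 or 60; control 35 or 50 (Section 6.1). Control pRR: 70–80% (Section 1.1.2.1). True difference: 0, or +10 points, the example improvement in Section 6.9.

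**Formulas.** Let d = p1 − p2.
- Wald with correction: d ± [1.96·√(p1q1/n1 + p2q2/n2) + ½(1/n1 + 1/n2)].
- Newcombe, from the Wilson limits (l, u) of each arm: lower = d − √[(p1 − l1)² + (u2 − p2)²]; upper = d + √[(u1 − p1)² + (p2 − l2)²].

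**One example, 16/20 against 28/35 (80% in both).**
- Standard error: √(0.16/20 + 0.16/35) = 0.1121; times 1.96 = 0.220.
- Correction: ½(0.0500 + 0.0286) = 0.039.
- Planned interval: ±0.259, width 0.518.
- Wilson limits: (0.584, 0.919) and (0.641, 0.900). Newcombe: (−0.238, 0.199), width 0.437.
- Miettinen-Nurminen: (−0.246, 0.208), width 0.454.
- The planned interval is 0.518/0.437 = 1.19 times the Newcombe width and 0.518/0.454 = 1.14 times the Miettinen-Nurminen width.

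**Exact coverage and mean width.** Each interval was evaluated at every pair of outcomes and weighted by its binomial probability.

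| n (exp v control) | True rates | Coverage, planned | Coverage, Newcombe | Width ratio |
|---|---|---|---|---|
| 20 v 35 | 75% v 75% | 97.1% | 94.8% | 0.542/0.453 = 1.20 |
| 20 v 35 | 85% v 75% | 97.6% | 95.4% | 0.491/0.423 = 1.16 |
| 40 v 35 | 75% v 75% | 96.9% | 95.4% | 0.440/0.381 = 1.16 |
| 60 v 50 | 75% v 75% | 97.0% | 95.2% | 0.358/0.318 = 1.13 |
| 60 v 50 | 85% v 75% | 96.9% | 95.0% | 0.334/0.298 = 1.12 |

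Over all six size pairs, with control at 70%, 75% or 80% and a difference of 0 or +10 points:
- coverage is 96.1–98.3% for the planned interval and 94.5–96.5% for Newcombe;
- mean width is 10–21% above Newcombe;
- with widths taken at the expected counts, the excess is 11.1–21.7% over Newcombe and 9.0–17.0% over Miettinen-Nurminen.

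The documents give no expected control ORR. For equal rates anywhere from 30% to 90%, the excess at expected counts is 7.9–23.1% over Newcombe and 5.3–18.3% over Miettinen-Nurminen.

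**High rates.** At 90% in both arms the excess over Newcombe is about 8%. At 95% in both, the ratio is 0.93–1.00, so there is none. With 92% in a 20-patient experimental arm and 98% in control, the planned interval covers 87% (20 v 20), 88% (20 v 35) and 81% (20 v 50), against 97–99.6% for Newcombe. (20 v 20 is below the planned control size.)

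**Strata.** Stratum sizes and rates are not in the documents. Assume four cells holding 40%, 40%, 10% and 10% of patients. With rates of 90/80/60/40%, the overall rate is 0.78, the total variance term 0.78 × 0.22 = 0.1716, and the within-cell term 0.4(0.09) + 0.4(0.16) + 0.1(0.24) + 0.1(0.24) = 0.148. The width ratio is √(0.1716/0.148) = 1.08. With equal rates it is 1.00. Ignoring the strata therefore costs 0–8% in width under these assumptions.

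**The case against.** The strongest reply is that nothing depends on this interval. Section 6.1 disclaims power and type I error, and expansion under Section 6.9 may use a posterior probability and rests on the totality of the data. A conservative, pre-specified interval is not invalid, and point estimates and counts are unaffected. All of that stands and limits the weight of the point.

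Several stronger readings do not stand:
- **That the interval collapses near the ceiling.** A reader might infer this because with 20/20 and 35/35 responders it is only ±½(1/20 + 1/35) = ±3.9 points, against (−16.1, +9.9) for Newcombe. The arithmetic is right, but both arms must be complete. For 20 v 35 the probability is 0.8^55 ≈ 5 in a million at 80% in both, about 5 in 100,000 at 90% v 80%, and 0.3% at 90% in both. With only one arm complete, 20/20 v 28/35, the planned interval is (0.028, 0.372) and Newcombe (0.011, 0.359), nearly the same width.
- **That the excess reaches 24% over Newcombe at these response rates.** This needs 20 v 20, and Section 6.1 plans at least 35 controls.
- **That this is the trial's only statement of precision.** Each arm also has a Clopper-Pearson interval.
- **That stratifying would repair the effect of changing allocation ratios.** Weighting over region and LDH does not adjust for enrolment period.

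Stratifying also has a cost. Four cells in a 20-patient arm average five patients, and some will hold fewer.

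**Conclusion.** The point holds as a modest improvement in calibration and precision. At the planned sizes, with control pRR at 70–80% and a difference of 0 or +10 points, the planned interval over-covers (about 96–98%) and is about 10–22% wider than Newcombe and about 9–17% wider than Miettinen-Nurminen. Newcombe needs none of that extra width to stay near 95%.

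The result rests on the cited control rate. If both arms respond at about 90% or more, the excess shrinks and then disappears. With very high, unequal rates, under-coverage in a 20-patient arm becomes possible, but this requires a control rate far above the one cited. The stratification part rests on assumed stratum sizes and rates and is worth little in width. Its main merit is that the analysis would follow the factors used to randomize.

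**What to change.** In Sections 6.4.1 and 6.4.2, replace the continuity-corrected Wald interval with a Newcombe or Miettinen-Nurminen 95% interval, and name which. Base it on a Mantel-Haenszel risk difference stratified by region and baseline LDH. State in advance how sparse cells are collapsed: the minimum cell size and the factor dropped first. Report the unstratified score interval alongside.

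If the strata prove too sparse, the unstratified score interval alone still improves on the plan; the text should then say that the analysis is unstratified and why.

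The cost is about one sentence in each section plus the collapsing rule, which is the only real burden. Standard software covers it, and no patient procedure or data collection changes.
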